## **12 STATISTICAL CONSIDERATIONS**

The following outlines the proposed statistical analyses methods planned as they relate to each research question (RQ).

• RQ1 Can a self-assessed hand dermatitis screening questionnaire for at-risk health care workers reliably be used as part of a health surveillance programme?

As the primary study outcome, we will calculate the sensitivity of the proposed selfassessment screening tool (single-item self-reported dermatitis) along with its 95% confidence intervals when compared with the gold standard (nurse's dermatitis assessment from the hand photographs). We will further assess its specificity, positive and negative predictive value. The analysis will be conducted for all participants and then separately by medium and high risk of hand dermatitis, determined by frequency of hand washing 10-20 times per day (medium risk), and more than 20 times per day (high risk).

• RQ2 What is the sensitivity and specificity of the hand dermatitis self-assessment screening questionnaire in identifying early hand dermatitis, and is it similar across all Fitzpatrick skin phototypes and occupational (clinical vs non-clinical) groups?

The accuracy of hand dermatitis self-assessment screening questionnaire will further be explored in sub- groups of our sample participants. Primarily sensitivity, and specificity, and further positive and negative predictive values, as indicators of the accuracy of the screening test will be estimated for clinical and non-clinical staff and their differences will be compared statistically. Due to the high number of NHS staff of non-white ethnic origin, and the lack of information about hand dermatitis or ability to self-report its presence across the six Fitzpatrick skin phototypes, we will also stratify our results by Fitzpatrick phototypes, with a potential to identify skin phototypes in which accuracy of the screening questionnaire is lower.

• RQ3 Is the self-assessment screening questionnaire and photographic method acceptable and feasible to use in healthcare staff in a busy NHS setting?

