#### 12.1 Statistical power

Considering as the primary study outcome the sensitivity of the single-item questionnaire (with secondary outcomes being its specificity, positive and negative predictive value) we enquired six occupational physicians with experience in NHS work what they would consider as the minimum acceptable sensitivity for such a self-assessment screening tool (single-item questionnaire) to be administered by managers to detect hand dermatitis in at risk healthcare workers. The majority (3 out of 4 who responded to our enquiry) reported a sensitivity of 80%. Assuming a prevalence of hand dermatitis among healthcare workers of 15%, and a high sensitivity of 0.90% with a width of confidence interval 0.10 (targeting a lower bound for sensitivity of 0.80), the estimated required sample size is 231. We hypothesised the same prevalence for clinical and non-clinical staff, and also for staff of light, medium and dark skin. This totals 1386 participants (i.e. 231 participants for each of the 6 groups clinical/non-clinical staff and type of skin), which would give sufficient power for any analysis stratification. We aim to recruit approximately equal numbers (~460 participants) from each of the 3 sites in the study.

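### The claim of sufficient power for any stratification is unsupported: 231 per cell is a one-group precision size, and sensitivity comparisons between groups have modest to low power

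*Protocol*

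**What the plan says.** Protocol section 12.1 names sensitivity as the primary outcome and sizes one group. It takes 15% of staff to be affected and works from "a high sensitivity of 0.90% with a width of confidence interval 0.10". The lower confidence limit is meant to reach 0.80, and the result is 231 participants. Prevalence is held equal across occupations and across three levels of skin colour ("and also for staff of light, medium and dark skin"). The 231 is then multiplied by the six cells of occupation by skin type. Of the resulting 1386, the section says that it is a number "which would give sufficient power for any analysis stratification".

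Section 12 sets out the analyses. Under RQ1, sensitivity is estimated "along with its 95% confidence intervals when compared with the gold standard", for all participants and then by medium and high hand-washing risk. Under RQ2, accuracy measures "will be estimated for clinical and non-clinical staff and their differences will be compared statistically". For skin type, where six phototypes are named, the text says "we will also stratify our results by Fitzpatrick phototypes", with the aim of finding phototypes in which accuracy is lower. RQ2 itself (section 4.1) asks whether accuracy is similar across phototypes and occupational groups.

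Section 7.1 specifies convenience sampling. Section 6.2 states an aim to represent different phototypes. No quota by occupation or phototype is given.

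**The concern.** A precision calculation fixes how wide the interval is within one group. It says nothing about the chance of detecting a difference between two groups, because it contains no difference and no power. Section 12.1 nevertheless draws a conclusion about power, and extends it to every stratification.

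The analyses in section 12 also do not match the groups that were sized. The sizing has three skin groups, the analysis has six phototypes, and no rule links them.

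RQ2 is at stake. The introduction wants the tool to work equally well across phototypes, and section 17 ties favourable findings to wider use in the NHS. A reader who trusts the power statement could take a non-significant comparison as evidence of equal sensitivity when the study had little chance of showing otherwise.

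**Working it through.** **Inputs.** From section 12.1: prevalence 0.15, sensitivity 0.90, target lower bound 0.80, 231 per cell, total 1386. From section 12: 95% intervals. Assumed here, because the protocol gives no such figures: a two-sided 5% test, a comparison of 0.90 with 0.80, equal groups, and no multiplicity adjustment.

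**1. The plan's own figure.** Cases = 1.96² × 0.90 × 0.10 / 0.10² = 34.57. Participants = 34.57 / 0.15 = 230.5, rounded up to 231; 231 × 6 = 1386. The figure reproduces only if 0.10 is the half-width; a full width of 0.10 would need 922. The formula has no between-group term and no power term.

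**2. Expected cases.** 1386 × 0.15 = 207.9 in all. Divided equally, that is 104.0 for each of two groups, 69.3 for each of three and 34.65 for each of six.

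**3. Precision of sensitivity.** Half-width = 1.96 × √(0.09 / cases).

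| Stratum (equal groups) | Cases | Half-width |
|---|---|---|
| All participants | 207.9 | 0.04 |
| Occupation (2) | 104.0 | 0.06 |
| Skin group (3) | 69.3 | 0.07 |
| Phototype, or sized cell (6) | 34.65 | 0.10 |
| Phototype × occupation (12) | 17.3 | 0.14 |

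A phototype with a 10% share of the sample (assumed) has 20.8 cases and a half-width of 0.13. With a 5% share (assumed) it has 10.4 cases and a half-width of 0.18.

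**4. Power for a difference in sensitivity.** Power = Φ[(d − 1.96 × se₀) / se₁], where se₀ = √(2 × p̄(1 − p̄) / m), se₁ = √([p₁(1 − p₁) + p₂(1 − p₂)] / m), p̄ is the mean of p₁ and p₂, and m is cases per group. For clinical v non-clinical staff at 0.90 v 0.80: se₀ = √(2 × 0.85 × 0.15 / 103.95) = 0.0495; se₁ = √(0.25 / 103.95) = 0.0490; (0.10 − 1.96 × 0.0495) / 0.0490 ≈ 0.06; power = 0.52.

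| Comparison | Cases each | 0.90 v 0.80 | 0.90 v 0.75 | 0.90 v 0.70 | Detectable at 80% |
|---|---|---|---|---|---|
| Clinical v non-clinical (planned) | 104 | 52% | 82% | 96% | about 0.15 |
| Two of three skin groups (if made) | 69 | 38% | 65% | 85% | about 0.19 |
| Two of six phototypes (if made) | 35 | 21% | 37% | 55% | about 0.28 |

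For 80% power at 0.90 v 0.80, 199 cases per group are needed: 199 / 0.15 = 1,327 participants per group, or 2,654 for two groups.

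**5. Imbalance.** If non-clinical staff are 10%, 20% or 30% of the sample (assumed) and have the higher sensitivity, power for 0.90 v 0.80 is 14%, 29% or 41%. If they have the lower sensitivity, it is 32%, 44% or 50%.

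**6. Specificity.** The same formula applied to the 85% without dermatitis, at 0.90 v 0.80 (also illustrative), gives over 99%, 98% and 79% for the three comparisons.

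**The case against.** The case for the protocol is substantial, and most of it stands as a limit on the point.

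- The arithmetic is sound, and six equal phototypes of 231 would each just meet the protocol's own half-width of 0.10. So would any other stratum of at least 231, including the hand-washing risk strata. A reader might infer that moving from three skin groups to six phototypes by itself breaks the design. It does not. Precision falls short only if phototypes are unequal or are crossed with occupation.
- A formal comparison is written only for clinical v non-clinical staff. For phototypes the plan says it will stratify, so the 38% and 21% describe tests that it does not specify.
- A reader might infer that a drop from 0.90 to 0.80 would usually be missed. At 52% power with equal groups, that is not so for the planned test. It holds for the skin comparisons, or if occupational groups are clearly unequal.
- The 0.10 difference is not the protocol's. There, 0.80 is a minimum acceptable value and a target lower bound. At 0.90 v 0.75 the planned test has 82% power.
- The protocol has no rule that a non-significant test means similarity, and the analysis plan may deal with this. The risk of misreading is therefore only a risk.

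None of this supports the sentence itself. It claims power, for any stratification, from a calculation that contains none.

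**Conclusion.** The sentence is wrong as written and should be corrected. The failure is confined to between-group comparisons of sensitivity. For the one planned test, power is 52% at a difference of 0.10 and reaches 80% only at about 0.15. Comparisons by skin group or phototype, if made, would be weaker, with detectable differences of about 0.19 and 0.28.

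These figures rest on 15% prevalence in every group, equal groups, a sensitivity of 0.90 in the better group and a two-sided 5% level. Unequal occupational groups lower the power in every split computed, and convenience sampling does not secure equal ones. It also does not secure 231 participants in each phototype.

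The missing link between three sized skin groups and six analysed phototypes is a separate gap in the same section. The sample size arithmetic and the overall sensitivity estimate are not in question. Specificity comparisons are well powered for occupation and for three skin groups, and close to 80% at 231 per group.

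**What to change.** In section 12.1, delete the power sentence and put in its place:

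- the expected half-widths for sensitivity: 0.06, 0.07 and 0.10 for two, three and six equal groups, with a note that phototype crossed with occupation gives about 0.14 and that small phototypes will be less precise;
- the differences in sensitivity detectable with 80% power: about 0.15, 0.19 and 0.28;
- a statement that between-group comparisons of sensitivity are exploratory;
- the rule that assigns the six Fitzpatrick phototypes to light, medium and dark skin.

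In section 12 under RQ2, state that group differences will be reported with 95% confidence intervals and that similarity will not be concluded from a non-significant test. While editing, print the sensitivity as 0.90 and call the 0.10 a half-width.

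The cost is wording in the protocol, carried into the analysis plan, and a less favourable statement of power. No extra participants are needed.

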#### **13 PEER REVIEW**

The research plan was developed with input from clinical academic researchers. The research plan (grant application) was independently assessed by experts in the field as part of the grant application process and satisfactory responses to peer reviewer feedback were collated and approved by the funding body (The Colt Foundation) prior to Health Research Authority submission.

### **14 FINANCING**

The Colt Foundation awarded funding of £70,450 to support conduct of this study. The funding period is two years and cover pay (salary) and non-pay costs (expenses).

#### **15 INSURANCE AND INDEMNITY**

This study is sponsored by Guy's and St Thomas' NHS Foundation Trust (GSTFT) and indemnity is provided through NHS Resolution's Clinical Negligence Scheme for Trusts (CNST) which provides indemnity for clinical negligence. In the case of negligent harm, health care professionals undertaking clinical trials or studies on volunteers, whether healthy or patients, in the course of their NHS employment are covered by NHS Resolution. In the case of non-negligent harm, legal liability does not arise where a person is harmed but no one has acted negligently. In exceptional circumstances NHS bodies may consider whether an ex-gratia payment could be offered.

#### **16 DATA CONTROLLER**

Guy's and St Thomas' NHS Foundation Trust is the Data Controller as defined by UK general data protection legislation (UK GDPR) for this study and as such agrees to comply with the obligations placed on a Data Controller by the UK GDPR. This is not limited to, but includes, being responsible for and able to demonstrate compliance with the principles relating to Processing of Personal Data (Article 5 UK GDPR).

#### **NHS Foundation Trust**

# **17 REPORTING AND DISSEMINATION**

#### 17.1.1 Potential relevance to policy and practice

If the findings from this study indicate that the single-item questionnaire with follow-up of those reporting possible hand dermatitis using teledermatology (selfie hand photographs taken with a mobile phone camera) is feasible, acceptable, and effective as a self-assessment screening tool in a workplace surveillance programme then we envisage the findings will have important relevance to policy and clinical practice of skin health surveillance programmes in the health service.

Most notably, the potential to implement this self-assessment screening tool more widely across the NHS workforce and to other high-risk worker groups will lead to improvements in the early detection and management of workers hand dermatitis, and such favourable outcomes will have wider benefits to the NHS. We are evaluating the health surveillance tool in the health service setting for pragmatic reasons, but since we are testing the tool in non-clinical staff, there is no reason why the results should not be generalisable to other industries such as care homes, hairdressing, and floristry where workers also have a high risk of developing hand dermatitis.

### 17.1.2 Dissemination

At the end of the study, we will convene a one-off stakeholder forum involving representatives from infection, prevention, and control (IPC), occupational health, NHS Employers, and the regulatory body (Health and Safety Executive) to consider the findings of the study and recommendations for the wider adoption of the self-assessment screening tool across the NHS if the results are favourable.

The findings from the research will be written up into a final study report (for the funder) and journal articles. Additionally, we will present the findings of this research at professional forums (Faculty and Society of Occupational Medicine Annual Scientific Meeting) and will disseminate findings via our research website. Additionally, we will provide a summary report to participating sites and participants who request this information.

**NHS Foundation Trust** 

# APPENDIX 1 SAE Reporting Flow Diagram-Non CTIMPs

# **APPENDIX 2**

Information with regards to Safety Reporting in Non-CTIMP Research

IRAS284234 Digital skin surveillance of healthcare workers in the NHS Protocol v1.0 15.05.25 Page **29** of **30** 

# NHS Foundation Trust

	Who	When	How	To Whom
SAE (related and unexpected)	Chief Investigator	-Report to Sponsor within 24 hours of learning of the event -Report to the MREC within 15 days of learning of the event	SAE Report form for Non- CTIMPs, available from NRES website.	Sponsor and MREC
Urgent Safety Measures	Chief Investigator	Contact the Sponsor and MREC Immediately Within 3 days	By phone	Main REC and Sponsor
			form giving notice in writing setting out the reasons for the urgent safety measures and the plan for future action.	Main REC with a copy also sent to the sponsor. The MREC will acknowledge this within 30 days of receipt.
Progress Reports	Chief Investigator	Annually (starting 12 months after the date of favourable opinion)	Annual Progress Report Form (non-CTIMPs) available from the NRES website	Main REC with a copy to be sent to the Sponsor
Declaration of the conclusion or early termination of the study	Chief Investigator	Within 90 days (conclusion) Within 15 days (early termination) The end of study should be defined in the protocol	End of Study Declaration form available from the NRES website	Main REC with a copy to be sent to the sponsor
Summary of final Report	Chief Investigator	Within one year of conclusion of the Research	No Standard Format However, the following Information should be included:- Where the study has met its objectives, the main findings and arrangements for publication or dissemination including feedback to participants	Main REC with a copy to be sent to the sponsor
